Health Burden:	Burden of the disease imposed on the study population in terms of incidence of the disease and associated healthcare utilization in any healthcare setting.
Healthcare settings (Healthcare Utilization):	Primary, secondary and tertiary care settings such as self- care with over-the-counter [OTC] drugs, general practitioner (GP) visits, emergency room (ER) visits, hospital visits, etc.
Interventional Human Subject Research:	Studies in which participants are administered medical care, medicinal products and/or medical/scientific procedures as described in a research protocol.
Passive Surveillance:	A contact initiated by the subject's parent/LAR, notifying the study physician / site staff of the occurrence of an event of interest.
Population Attributable Risk:	Population attributable risk is the portion of the incidence of a disease in the population (exposed and unexposed) that is due to exposure. It is the incidence of a disease in the population that would be eliminated if exposure were eliminated.
Population Attributable Risk Percent:	Population attributable risk percent is the percent of the incidence of a disease in the population (exposed and unexposed) that is due to exposure. It is the percent of the incidence of a disease in the population that would be eliminated if exposure were eliminated.
Prospective study:	A study in which the subjects/cases are identified and then followed forward in time in order to address one or more study objectives.
Research protocol:	A document that describes the objective(s), design, methodology, statistical considerations, and organization of a study. The protocol usually also gives the background and rationale for the study, but these could be provided in other protocol referenced documents.
Self-contained study:	Study with objectives not linked to the data of another study.

	200150 (EPI-RSV-005 BOD) Protocol Amendment 3 Final
Seroprevalence:	The total number of cases within the study population at a specific time that test positive for the disease based on blood serum specimens.
Site Monitor:	An individual assigned by the Sponsor who is responsible for assuring the proper conduct of epidemiological studies at one or more investigational sites.
Study population:	Sample of population of interest.
Sub-cohort:	A subgroup of the total cohort of study subjects for whom the planned study procedures are different from those planned for the other study subjects.

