1.1.2. Asthma

Infant respiratory viral infection and childhood asthma are the most common acute and chronic diseases of childhood, respectively. Common clinical features and links between these diseases have long been recognized, with early-life RSV LRTIs being strongly associated with increased asthma risk.

Although asthma is probably a heterogeneous disease or syndrome, three factors and/or events consistently emerge for their ability to significantly influence asthma inception in the first decade of life: immune response aberrations, which appear to be defined best by the concept of cytokine dysregulation; LRTIs, in particular RSV; and some form of gene–environment interaction that needs to occur at a critical timeperiod in the development of the immune system or the lung [Lemanske, 2002].

Population-level contribution of RSV LRTIs is best demonstrated by the populationattributable risk for asthma after these early-life LRTIs. Among infants, the cumulative incidence of LRTI is approximately 18 to 32% in the first year of life and approximately 9 to 17% in the second year of life. Among infants with LRTI, the prevalence of RSV can be as high as 80%, especially in the first 3 months of life. Thus, the phenotype of asthma after infant RSV LRTI accounts for up to 31% of early childhood asthma, with a population-attributable risk estimated at about 13% in several diverse populations [Feldman, 2015].

Numerous longitudinal studies have demonstrated this first important line of evidence that RSV LRTIs precede the development of asthma. Several birth cohort studies also demonstrate a dose–response relationship between infant respiratory viral infection severity and asthma risk, with increasing infant infection severity associated with greater childhood asthma risk and asthma severity [Feldman, 2015].

The Childhood Origins of Asthma (COAST) study was developed to determine and define the importance of these three factors on asthma pathogenesis and to test different asthma case classifications [Lemanske, 2002; Lemanske, 2005; Bisgaard, 2011; Jackson, 2008; Jackson, 2012; Bønnelykke, 2015]. These studies have used similar albeit slightly different case definitions on asthma diagnosis. The International Study of Asthma and Allergies in Childhood (ISAAC) takes a slightly different parentbased questionnaire approach toward assessing asthma prevalence in young children.

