4. CASE DEFINITIONS (AMENDED 15-DEC-2017)

4.1. Primary Study

DEFINITIONS FOR LRTI SURVEILLANCE:

During the surveillance for LRTI, a case is defined as;

A child suffering from a potential LRTI.

Potential LRTI:

Suspected involvement of the lower respiratory tract if a child with clinical signs of RTI, defined as either a runny nose, blocked nose or cough, is believed to have difficulties in breathing in the opinion of the investigator/study staff, based on the symptoms reported by the parent(s)/LAR(s) during the surveillance phone contacts. Difficulty in breathing as suspected by the investigator/study staff through reported symptoms will then be objectively confirmed by the investigator/study staff by means of pulse oximetry and RR at an examination visit. If at least one of these parameters is outside of the pre-defined normal range (Refer to Table 3), the case will be considered as an LRTI for the surveillance part of the study.

A subject is considered to have difficulty in breathing if he/she shows signs of:

- Wheezing or stridor
- Tachypnea
- Flaring (of nostrils)
- Chest indrawings
- Apnea

Table 3 Normal ranges for RR and Sa02

RR	Sa02
\leq 60/min for a child below 2 months of age	\geq 95%, independent of the age of the child
\leq 50/ min for a child aged 2 - 11 months	
\leq 40/min for a child aged 12 - 24 months	

RR= Respiratory Rate; SaO2= Blood Oxygen Saturation; min = minutes

During the surveillance for LRTI, any potential LRTI that is not found to meet the criteria for an LRTI may need a subsequent objective assessment by the investigator/study staff.

Note: The investigator/study staff will do an initial assessment of a case reported for the examination visit as either RTI or LRTI, only to determine further study activities. The final classification of all the cases reported as either, RTI, LRTI or severe LRTI will be done during statistical analyses as per the definitions given below.

CASE DEFINITIONS FOR DATA ANALYSIS:

LRTI case definition and severity scale

During the analysis of the study on the full dataset available for each case, all cases identified during the surveillance for LRTI will be definitively classified as either RTI, LRTI or severe LRTI according to the LRTI case definition and severity scale described in Table 4, and also according to the classification of WHO and the classification used by Nokes *et al* [Modjarrad, 2016; Nokes, 2004] (see below).

RTI	LRTI	severe LRTI

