4.2. Extension Study

Table 5 presents the case definitions of wheeze and asthma. The Bisgaard and Jacksoncase definitions have been updated so as to better account for advances in asthmatreatment options while still preserving the case definitions' core intent.

200150 (EPI-RSV-005 BOD) Protocol Amendment 3 Final

	Definition	Reference
Episode of reported wheeze	Parents report a whistling sound associated with labored breathing	NA
Medically attended wheeze	An episode of health care provider confirmed wheeze	NA
Wheeze or asthma requiring hospital admission	An episode of health care provider confirmed wheeze requiring hospital admission	NA
Recurrent wheeze	This will be defined as four or more episodes of wheeze in one year. These episodes may be parent reported wheeze or health care provider confirmed wheeze.	[Morgan 2005]
Asthma case definition 1	Asthma will be defined at annual review based on the documented presence of one or more of the following characteristics in the previous year: (1) provider diagnosis of asthma (2) Use of a short acting beta agonist (e.g., albuterol) for coughing or wheezing episodes as prescribed by a health care provider (3) use of a daily controller medication (4) step-up plan including use of a short acting beta agonist (e.g., albuterol) or short-term use of inhaled corticosteroids during illness (5) use of oral and/or systemic steroids for asthma exacerbation	Based on [Jackson, 2008]
Asthma case definition 2	 Asthma will be defined at annual review based on parent interview and review of medical records with the presence of all of the following: (1) recurrent episodes of troublesome lung symptoms (wheeze or whistling sounds, breathlessness, or recurrent troublesome cough severely affecting the well-being of the infant occurring with a frequency of 5 episodes within 6 months period or 4 weeks of consecutive symptoms); (2) symptoms typical of asthma (recently proposed to be termed multitrigger wheeze; e.g., exercise-induced symptoms, prolonged nocturnal cough, recurrent cough outside the common cold, and symptoms causing wakening at night); (3) intermittent rescue use of inhaled β2-agonist; (4) symptoms controlled by daily inhaled corticosteroids 	Based on [Bisgaard, 2011]

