9.8. Analysis of Objectives for the Extension study

9.8.1. Primary objectives: none

9.8.2. Secondary objectives

Data for secondary endpoints may be pooled across the primary and extension periods. Additional details are provided in the SAP.

9.8.2.1. To determine the population attributable risk of wheeze and asthma from birth to sixth birthday due to RSV clinical LRTI in the first two years of life.

The incidence rate of medically attended wheeze, wheeze or asthma requiring hospital admission, and prescription of medications for wheeze or asthma may be calculated and stratified by country.

The population attributable risk *may be* calculated by subtracting the incidence rate in the subjects who did not have RSV clinical LRTI in the first two years of life from the incidence rate in all subjects including both who had and who did not have RSV clinical LRTI in the first two years of life.

Details will be provided in the SAP. An example follows.

The population attributable risk of medically attended wheeze may be calculated as:

Ip-Iu

Where Iu is the incidence rate of medically attended wheeze in subjects who did not have RSV clinical LRTI in the first two years of life, and Ip is the incidence rate of medically attended wheeze in all subjects including both who had and who did not have RSV clinical LRTI in the first two years of life. *The above population attributable risk formula may be further adapted to best accommodate the data and their required analytic assumptions (e.g., a modified formula may be used for population attributable risk calculations involving recurrent outcomes).*

9.8.2.2. To determine the population attributable risk percent of wheeze and asthma from birth until sixth birthday due to RSV clinical LRTI in the first two years of life.

The population attributable risk percent together with 95% CI of medically attended wheeze, wheeze or asthma requiring *hospital* admission, and prescription of medications for wheeze and asthma *may* be calculated overall and by age strata (0-2 years, 2-4 years and 5-6 years), respectively.

The population attributable risk percent *may be* calculated by dividing the population attributable risk by the incidence rate in all the subjects including both who had and who did not have RSV clinical LRTI in the first two years of life.

For example, the population attributable risk percent of medically attended wheeze *may* be calculated as:

(Ip-Iu)/Ip*100

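### In Protocol 9.8.2, wheeze from the RSV LRTI that makes a child exposed can also count as an outcome, so the 0-2 year and birth-to-6 PAR mix acute illness with subsequent wheeze

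*Protocol*

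**What the plan says.** Protocol 9.8.2.1 sets out to estimate the "population attributable risk of wheeze and asthma from birth to sixth birthday due to RSV clinical LRTI in the first two years of life". PAR is Ip minus Iu, where Ip is the rate in all children and Iu is, in the worked example, the "incidence rate of medically attended wheeze in subjects who did not have RSV clinical LRTI in the first two years of life". Exposure is thus a fixed ever/never label, assigned by age 2. Section 9.8.2.2 divides the difference by Ip to give PAR%, which may "be calculated overall and by age strata (0-2 years, 2-4 years and 5-6 years"). Section 9.8.2 also states that "Data for secondary endpoints may be pooled across the primary and extension periods".

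The outcome in Table 5 (section 4.2) is broad. Medically attended wheeze is "An episode of health care provider confirmed wheeze", with no exception for wheeze during an RSV LRTI. The other two secondary endpoints (section 9.2.2) are hospital admission and prescription medication for wheeze or asthma.

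In section 4.1 the first listed sign of difficulty in breathing is "Wheezing or stridor". Under sections 6.5.12 and 6.5.16, suspected difficulty in breathing with RTI symptoms leads to the examination visit, where the nasal swab is taken. Section 3.1 confirms that wheeze was documented in the primary study. In the SAP (11.2.2.1 and 11.2.1.4.1), parent-reported wheezing counts as difficulty breathing and can meet Component A of the WHO LRTI definition.

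The protocol defers PAR details to a SAP. The supplied SAP says in section 2.1 that it does not describe the extension analyses.

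**The concern.** One wheezing RSV LRTI can do two jobs. It classes the child as exposed, and it supplies a medically attended wheeze, perhaps with an admission and a bronchodilator prescription. A never-exposed child cannot contribute such an event, so it raises Ip and leaves Iu alone.

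The order of events is also open. A child who wheezes at 5 months and has a first RSV LRTI at 18 months brings the earlier wheeze into the exposed group.

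PAR and PAR% are the extension's only secondary objectives, and it has no primary objective. The study title speaks of the development of wheeze and asthma, and section 1.2 foresees use of the results to judge a vaccine's public health impact. A reader could take acute RSV wheeze, which the primary study already measures as RSV burden, for evidence that RSV LRTI leads to subsequent wheeze.

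**Working it through.** **Stated figures.** The protocol gives no expected PAR and no precision for it. Its planning figures do reproduce:
- enrolment: 1920/(1 − 0.20) = 2400
- design effect: 1 + (160 − 1) × 0.02 = 4.18
- exact Poisson interval for 6 cases in 320 child-years: 6.9 to 40.8 per 1000

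**Inputs.**
- p, the share of children with RSV LRTI by age 2. Section 9.3 uses 20 hospitalizations per 1000 child-years as an example and expects the RSV LRTI rate to be 8 times the hospitalization rate: 20 × 8 = 160 per 1000. Using p = 0.16 treats this first-year rate as the two-year share, which is an approximation. Range tried: 0.10 to 0.35.
- w, the share of those episodes with provider-confirmed wheeze. Not in the documents; assumed 0.5, range 0.25 to 0.75.
- λ, background wheezes per child-year, equal in all children. Not in the documents; assumed 0.2, range 0.1 to 0.4.
- T, years in the window: 2 or 6.

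**Formula**, if RSV LRTI has no effect on subsequent wheeze: Iu = λ and Ip = λ + pw/T. Hence PAR = pw/T and PAR% = pw/(pw + λT).

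**Result.** pw = 0.16 × 0.5 = 0.08.
- 0-2 years: PAR = 0.08/2 = 0.04, or 4.0 per 100 child-years. PAR% = 0.08/(0.08 + 0.40) = 16.7%.
- Birth to 6: PAR% = 0.08/(0.08 + 1.20) = 6.25%.

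The corners of the ranges are:

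| p, w, λ | 0-2 years | Birth to 6 |
|---|---|---|
| 0.10, 0.25, 0.4 | 0.025/0.825 = 3.0% | 0.025/2.425 = 1.0% |
| 0.35, 0.75, 0.1 | 0.2625/0.4625 = 56.8% | 0.2625/0.8625 = 30.4% |

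**Simulation** (1920 children, 400 runs, same null and base values; simulation intervals in brackets):

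| Analysis | Mean PAR% |
|---|---|
| As written, 0-2 | 16.6 (13.2 to 20.0) |
| As written, birth to 6 | 6.2 (4.3 to 8.0) |
| First event only, 0-2 | 17.2 (14.0 to 20.6) |
| First event only, birth to 6 | 9.1 (7.1 to 11.2) |
| Index episode excluded, 0-2 | 0.0 (−3.2 to 3.1) |
| Index episode excluded, birth to 6 | 0.0 (−1.7 to 1.6) |
| Outcomes from the second birthday | 0.0 (−2.2 to 2.1) |
| Time-varying exposure, index episode excluded, birth to 6 | 0.0 (−1.6 to 1.4) |
| Wheeze before the LRTI only | −0.1 (−2.1 to 2.4) |

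The last row shows that earlier wheeze alone does not push the PAR upward. It does so only when children share a susceptibility to both events. With an assumed gamma frailty of variance 0.5 and no index-episode wheeze, earlier wheeze gives 4.3% (1.3 to 7.6). The 2-6 year PAR% is then 8.3% (5.4 to 11.5) as well. That is confounding, and starting the count at age 2 would not remove it.

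**The case against.** The best defence is that acute wheeze belongs in the figure. It is caused by the RSV LRTI. The Glossary says of PAR: "It is the incidence of a disease in the population that would be eliminated if exposure were eliminated". Section 1.2 refers to total burden up to the sixth birthday, and section 2.2.2 frames the objectives from birth. This stands. A reader might infer that the PAR is positive with no causal effect at all; the documents do not support that, and the null here is only that subsequent wheeze is unaffected. What the defence does not justify is one unlabelled figure that carries both quantities.

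Second, uncontaminated results are already planned. The 2-4 and 5-6 year strata and the asthma regression in 9.8.3.2 fall after the exposure window. This stands too, so it would be wrong to conclude that the whole extension analysis is compromised.

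Third, the text is permissive. Pooling and the PAR calculation are optional, and the formula may be adapted. This makes the point an open gap rather than a fixed rule. Still, only one formula is given, and its example of adaptation is recurrent outcomes, not the order of exposure and outcome.

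Fourth, section 2.2.2 names recurrent wheeze, which Table 5 defines as at least four episodes in a year; a single index episode cannot meet that. True, but the secondary endpoints in 9.2.2 do not require recurrence.

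Finally, the extension has no primary objective and all analyses are descriptive. That limits the consequences but does not settle what the figure means.

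**Conclusion.** The point holds for the 0-2 year and the overall birth-to-6 PAR and PAR%. As written, they can combine the acute RSV episode with subsequent wheeze, and they would be positive with no effect on subsequent wheeze. The illustrative size is about 17% at 0-2 years and 6% from birth to 6, with ranges of 3.0-56.8% and 1.0-30.4%. These figures rest on an assumed wheeze share and background rate, on p approximated from the planning rates, and on counting the index episode under the permissive wording.

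Two further inferences are not supported. Wheeze before the LRTI is a flaw of temporal order, but it does not by itself bias the PAR upward. A reader might also set the 17% beside the "population-attributable risk estimated at about 13% in several diverse populations" in section 1.1.2 and conclude that the artefact matches the expected signal. That figure is for asthma, while the calculation here is for wheeze episodes, so the two are not like for like.

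**What to change.** In Protocol 9.8.2 and the extension SAP:

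- Add a PAR and PAR% for subsequent wheeze, on outcomes from the second to the sixth birthday as one continuous window. The listed strata leave the year between 4 and 5 unclear. Rest any statement about development of wheeze or asthma on this result.
- For any 0-2 year or from-birth figure, also report it with RSV LRTI as a time-varying exposure and with events inside the RSV LRTI episode excluded. The episode runs from its start date to its end date plus the 7 symptom-free days. SAP 11.2.1.4.7, 11.2.1.4.8 and 11.2.1.12 already derive these dates and apply the 7-day rule.
- Show acute wheeze during RSV LRTI separately.
- Keep the unrestricted from-birth PAR if wanted, labelled as total burden including the acute episode.

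The objective framed from birth can stay. The cost is some wording, a little more analysis, fewer outcome events and a smaller PAR for subsequent wheeze. The change does not address confounding by shared susceptibility.

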9.8.3. Tertiary objectives

9.8.3.1. To explore the association of RSV clinical LRTI in the first two years of life and other potential risk factors for wheeze and asthma

Endpoints such as medically attended wheeze, wheeze or asthma requiring *hospital* admission, and prescription of medications for wheeze or asthma *may be calculated as recurrent events and* stratified by country.

Occurrence/recurrence rates will be calculated overall and by subgroups *for each of the outcomes, as relevant.* Multivaria*ble* Poisson regression *or other appropriate* models

including RSV clinical LRTI in the first two years of life and other potential risk factors such as, but not limited to, family history of asthma, and/or allergies, contact with pets, child history of allergy, eczema or atopic dermatitis, etc., will be explored, respectively.

9.8.3.2. To explore the performance of asthma case definitions.

The number and percentage of children with diagnosis of asthma (case definitions 1, 2, *and 3* will be described for each *applicable* age; the number and percentage of children with recurrent wheeze *at each applicable age* will be described overall and by country in frequency tables.

The risk of asthma at the age of 6 years using case definitions 1, 2 and 3 (occurring from 2^{nd} to the 6th birthday) will be analyzed using multivaria**ble** logistic regression model including RSV clinical LRTI in the first two years of life and other potential risk factors listed above, respectively.

- Statistical analysis of agreement will be performed to compare *asthma* case definitions *1*, *2*, *and 3 to each other*.
- Cohen's kappa *(or other appropriate)* coefficient *may be used for the comparisons*. The magnitude of the kappa coefficient represents the proportion of agreement greater than that expected by chance.

9.9. Interpretation of analyses

All analyses will be descriptive with the aim to characterise overall occurrences, patterns and potential differences between groups in the endpoints related to the objectives.

The tertiary objective 'To explore the impact of changes to the symptoms and threshold levels of symptoms in the LRTI case definition and severity scale' will be assessed if we detect potential areas of improvement of the LRTI case definition and severity scale, such as clearly under or overestimated incidence rates of LRTI/ severe LRTI compared to the rates in the literature or a lack of discriminative power between severe and non-severe cases. This decision will not be taken on specific pre-defined thresholds.

9.10. Conduct of analyses

Analytic plans may be modified as appropriate to accommodate final sample sizes and data distributions. Any deviation(s) or change(s) from the original statistical plan outlined in this protocol will be described and justified in the final study report.

9.11. Sequence of analyses

An interim analysis will be performed after data lock at the end of recruitment (expected after 18 months) or in June 2015 whichever occurs first, on the data collected for the subjects recruited in the first year of the study (approximately 1600). This interim analysis will be performed to obtain preliminary indications of the results in very young infants. These preliminary results will be used for potential adjustment of the LRTI Case

Definition and Severity Scale before final analysis, and to provide data for other relevant decision making, as soon as possible.* The results pertaining to this analysis will be descriptively reported in *an* interim statistical report.

*Based on the preliminary results of the interim analyses it was decided that the incidence rate would be more robust if all subjects completed the primary study until 2 years of age.

Final analysis will be performed on all the data collected and cleaned in the study, at the end of the extension period which is expected to occur 7 years after study start. An integrated study report presenting the consolidated analysis for the entire study duration (primary and extension study period [as applicable]) will be written and made available to the investigators.

